6.1.6. Dose Adjustments/Modifications/Delays

No dose modifications are allowed for devimistat in this study.

The dose of Folinic Acid is not modified for any toxicity but is omitted if fluorouracil is omitted. Once a dose of any of the drugs comprising FFX is decreased, re-escalation of the dose is not permitted. Patients are taken off the study if they develop the same Grade 4 toxicity despite dose reduction. The dose adjustment scheme for FFX is dependent on the type of toxicities, as described below.

Hematologic Toxicity

Once hematologic toxicity is observed in a patient, do not retreat the patient with mFFX or FFX until the absolute neutrophil count is $\geq 1.5 \times 10^9/L$ and the platelet count is $\geq 75 \times 10^9/L$. The dose modification schemes for FFX related to hematologic toxicity are shown in Table 9.

Primary prophylaxis with myeloid growth factor will be at the discretion of the treating physician and as per the ASCO guidelines. If the patient is not being treated with myeloid growth factor the initial modification for neutropenia should be the addition of a myeloid growth factor. If the patient is already on a myeloid growth factor, then dose adjustments are as outlined in Table 9.

Table 9 Dose Modifications for Hematological Toxicities on Day 1 of a Cycle. Cycles are Every Two Weeks.

Day 1	Delay the Start of a Treatment Cycle*	Doses Reduction		
		Irinotecan	Oxaliplatin	Fluorouracil (5-FU)
ANC <1.5x10 ⁹ /L	Withhold treatment until granulocytes ≥1.5x10 ⁹ /L.	1 st occurrence: Continue same dose	1 st occurrence: Continue same dose	1 st occurrence: Delete bolus 5-FU
		2 nd occurrence: Reduce to 80% of starting dose	2 nd occurrence: Continue same dose	
		3 rd occurrence: Reduce to 50% of starting dose	3 rd occurrence: Reduce to 80% of starting dose	
		4 th occurrence: Discontinue irinotecan	4 th occurrence: Continue on 80% of starting dose	
Platelets <75x10 ⁹ /L	Withhold treatment until platelets ≥75x10 ⁹ /L.	1 st occurrence: No dose reduction	1 st occurrence: No dose reduction	1 st occurrence: Delete bolus 5-FU
		2 nd occurrence: Reduce to 80% of starting dose	2 nd occurrence: Reduce to 80% of starting dose	
		3 rd occurrence: Reduce to 50% of starting dose	3 rd occurrence: Discontinue oxaliplatin	
		4 th occurrence: Discontinue irinotecan	4 th occurrence: Discontinue oxaliplatin	

Table 10 Dose Adjustments According to Non-Hematological Toxicities (Excluding Alopecia, Nausea and Vomiting).

Adverse Events	Dose Reduction for Subsequent Treatment Cycles

Diarrhea Grade 3-4, or diarrhea + fever and/or neutropenia Grade 3-4
 
Patients must be instructed in the use of loperamide as treatment for diarrhea and must have a supply of this drug upon starting treatment. Patients should not be retreated with irinotecan until diarrhea is \leq Grade 1 (without loperamide for at least 24 hrs.).
 
If acute cholinergic syndrome appears (defined as early diarrhea and certain other signs and symptoms such as sweating, abdominal cramps, miosis and salivation), atropine sulphate (0.25 mg subcutaneously) should be administered unless clinically contraindicated. In patients who experienced an acute and severe cholinergic syndrome, the use of prophylactic atropine sulphate is recommended with subsequent doses of Irinotecan hydrochloride.
	
1st occurrence: Reduce the irinotecan dose to 80% of the original dose and delete the bolus 5-FU dose
 
2nd occurrence: Reduce also the oxaliplatin dose to 80% of the original dose AND reduce the dose of continuous 5-FU to 75 % of the original dose
 
3rd occurrence: Discontinue treatment

Mucositis or “Hand-Foot” Syndrome
	
Grade 1-2 toxicity - continue on same doses of drugs
 
Grade 3-4 toxicity - delete bolus 5-FU and a reduction of 25% in continuous 5-FU doses in subsequent treatment cycles.
 
If mucositis is related to oxaliplatin, delay oxaliplatin or modify the dose until the toxicity grade \leq 1.

Myocardial Ischemia – Monitored by Cardiac Enzymes (CK/CKMB, TP)
	
5-FU must be permanently discontinued.

Hyperbilirubinemia
	
Obstruction of the biliary system or progressive disease must be established, and the treatment cycle delayed if the cause is biliary obstruction that can be addressed to reduce the hyperbilirubinemia. If bilirubin is persistently $>1.5x$ of Upper Limit of Normal (ULN), irinotecan must be omitted. If there is no potentially reversible obstruction, then irinotecan must be discontinued.

Other Toxicities
	
To be discussed with Medical Director.

7.1. Study Procedures/Evaluations

7.1.1. Study Specific Procedures

Medical History:

Will be obtained by direct interview with the patient during the course of standard clinic visits or hospital admission.

Physical Examination:

Will be obtained during the course of standard clinic visits or hospital admission.

ECOG Performance Status scales¹⁹ will be used to assess how a patient's disease is progressing and assess how the disease affects the daily living abilities of the patient. The scale is listed in Table 11 below.

Table 11 Scales Used in ECOG Performance Status Grade

ECOG Score	Description
0	Fully active, able to carry on all pre-disease performance without restriction
1	Restricted in physically strenuous activity but ambulatory and able to carry out work of a light or sedentary nature, e.g., light housework, office work
2	Ambulatory and capable of all self-care but unable to carry out any work activities. Up and about more than 50% of waking hours
3	Capable of only limited self-care, confined to bed or chair more than 50% of waking hours
4	Completely disabled. Cannot carry on any self-care. Totally confined to bed or chair
5	Dead

Radiographic or Other Imaging Assessments:

Tumor Assessment:

Objective response assessment will be determined by triphasic contrast CT of the chest abdomen and pelvis as per RECIST guideline version 1.1 every 8 weeks +/-7 days while patients are on treatment. MRI assessments of tumor status may replace CT scans if needed for tumor response evaluation. However, the same imaging modality must be followed serially. Target lesions will be identified and documented prospectively from the baseline scan prior to assessments of any follow up scans. Each tumor lesion will be assigned a unique identifier consisting of the patient

study ID number followed by a letter. Should a lesion completely resolve during treatment that lesion will be scored as a 0 (zero) and not left blank to ensure lesion resolution is accurate and not a reflection of missing data. The timing and location of any new lesions will be recorded upon evaluation of the first scan to demonstrate this lesion. Patients will continue on assigned treatment until one of the stopping criteria are met (see Section 5.3.1). Patients who are allergic to contrast should get an MRI and those allergic to both, they can get a non-contrasted study.

The patient's best response within the first 12 cycles of treatment as determined by the independent assessment will be used in the recording of the ORR for each patient. OS will be monitored every 2 months via telephone contact after treatment termination. (Note: During post-study treatment telephone contact, information related to cancer treatment received after the study will also be collected). OS will be calculated from the day of randomization. The duration of OS will be measured until the date of death or censored at follow-up. Patients who are lost to follow-up, withdraw from follow-up or alive and progression free will be censored at the date of last follow-up for OS.

Progression free survival (PFS) is calculated from the date of randomization to the date of progressive disease or death from any cause. Patients who have neither progressed nor died will be censored at the day of their last radiographic tumor assessment, if available, or date of randomization if no post initiation radiographic assessment is available. If death or PD occurs after 2 or more missing radiographic visits, censoring will occur at the date of the last radiographic visit that the patient was known to be alive and progression-free.

Duration of response is calculated from the date of randomization to the date of confirmed clinical/radiological progression or death from any cause.

Biological Specimen Collection and Laboratory Evaluations:

Up to 10 unstained slides will be submitted when available from the pre-study diagnostic biopsy and the study's progression of disease biopsy (if available).

Blood Sampling for Pharmacokinetic (PK) Analysis:

PK sampling will occur only for the study Arm 1: devimistat + mFFX because the dosing level of Oxaliplatin and Irinotecan between mFFX (in Arm 1) and FFX (in Arm 2) are different. As such, PK comparison of components between mFFX and FFX is not appropriate and therefore no PK sampling for the study Arm 2: FFX.

Upon randomization through the interactive web response system (IxRS) system, a patient will be designated with a code assignment for blood sampling for PK analysis of devimistat and its metabolites CPI-2850 and CPI-1810. Assignment will be to blood sampling for either A) Full PK Analysis or B) Sparse PK Analysis. Assignment to group A will be dependent on hospital site, ability, experience and facility to collect a more detailed blood profile over a 48-hour window. A patient is considered evaluable post one time point after infusion for PK analysis.

A. Full PK Analysis Sampling

Upon enrollment through the IxRS system, a patient may be assigned a code for blood sampling for full PK Analysis. One goal of Full PK sampling on Cycle 1, Day 1 will be able to detail the peak plasma concentration (C_{max}), area under the plasma concentration versus time curve from time 0 to t (AUC_{0-t}), area under the plasma concentration versus time curve from time 0 to infinity (AUC_{inf}), elimination half-life ($T_{1/2}$), time to reach the maximum plasma concentration (T_{max}), clearance (CL), and volume of distribution (V_d) after the first dose and multiple doses of devimistat to fully characterize PK profiles of both the parent drug (devimistat) and its major metabolites (CPI-2850 and CPI-1810). The other goal of Full PK sampling on Cycle 1, Day 3 will be to evaluate devimistat and metabolite accumulation following multiple dosing during the course of multiple rounds of treatment through the assessment of Day 3 / Day 1 accumulation ratios (R) for C_{max} and AUC_{0-t} . A Table 12 of time points to sample is following.

Table 12 Full PK blood sampling schedule. Time points are counted from the start of CPI-613® (devimistat) IV infusion.

Cycle # Day #	Time point	N	Comment
Cycle 1, Day 1	0 hr. ±15 min (pre-dose)	15 patients in Arm 1 (devimistat + mFFX)	Pre-infusion
	0.25 hr. ±15 min		
	0.5 hr. ±15 min		
	1 hr. ±15 min		
	2 hr. ±15 min		
	2.5 hr. ±15 min		
	3 hr. ±15 min		
	4 hr. ±15 min		
	6 hr. ±15 min		

Cycle 1, Day 3	0 hr. ±15 min (pre-dose)	15 patients above	Pre-infusion
	0.25 hr. ±15 min		
	0.5 hr. ±15 min		
	1 hr. ±15 min		
	2 hr. ±15 min		
	2.5 hr. ±15 min		
	3 hr. ±15 min		
	4 hr. ±15 min		
	6 hr. ±15 min		

B. Sparse PK Analysis Sampling

Upon enrollment through the IxRS system, in the pool of remaining patients in Arm 1: devimistat + mFFX, a patient may be assigned a code for blood sampling for “sparse” Population PK analysis. Patients will be randomly assigned to one of the following 12 groups for sparse PK sampling where each group will be sampled at a single time point within 0-24 hours counted as starting from IV infusion on the day selected by IxRS. Each group will be composed of approximately 18-20 patients.

Table 13 Sparse PK blood sampling schedule. Time points are counted from the start of CPI-613® (devimistat) IV infusion.

Group #	Cycle #	Time point Window
1	Cycle 1	Day 1: 0-24 hr.*
2	Cycle 2	Day 1: 0-24 hr.*
3	Cycle 3	Day 1: 0-24 hr.*
4	Cycle 4	Day 1: 0-24 hr.*
5	Cycle 5	Day 1: 0-24 hr. *
6	Cycle 6	Day 1: 0-24 hr.*
7	Cycle 7	Day 1: 0-24 hr.*
8	Cycle 8	Day 1: 0-24 hr.*
9	Cycle 9	Day 1: 0-24 hr. *
10	Cycle 10	Day 1: 0-24 hr.*
11	Cycle 11	Day 1: 0-24 hr.*
12	Cycle 12	Day 1: 0-24 hr.*

*One blood sampling at the patient/sites choosing during the time point window

In addition to measurement of the study agent and metabolites, plasma concentrations of the components of the mFFX and FFX standard of care regimen will also be evaluated.

All PK samples should be shipped to the Central Lab. Mailing address, contact name and phone number will be provided in laboratory manual.

The bioanalytical assays using validated LC/MS/MS methods for the parent drug devimistat and metabolites CPI-2850 and CPI-1810, as well as components of mFFX, will be provided in laboratory manual.

Cardiac marker (Troponin I)

As PANC003 is a Phase III trial for CPI-613[®] (devimistat) in pancreatic cancer, every effort should be made to ensure sites, investigators and patients comply with the study protocol for evaluation of elevated Troponin I. 24 patients in each arm (Arm 1 and Arm 2) will be evaluated for elevated Troponin I.

Troponin I testing should occur within 24 hours prior to the first dose (Cycle 1, Day 1) of study treatment dosing, but no sooner than 30 minutes prior to dosing. This does not require an extra sample collection, as other labs are collected at the same time point.

Troponin I testing should occur after the completion of all study medications. This will require an additional blood sample.

The schedule is detailed below.

ARM 1: CPI-613[®] (devimistat) + mFFX

Phase, Cycle, Day	Time Points	N	Comment
Cycle 1, Day 1	0 hr (up to 30 min pre-dose)	24 patients	Pre- CPI-613 [®] (devimistat) infusion
Cycle 1, Day 3	After completion of last dose of all study drugs (+ 30 min)*	24 patients	Post- CPI-613 [®] (devimistat) infusion

*This test for Troponin I will require an additional blood sample.

ARM 2: FFX

Phase, Cycle, Day	Time Points	N	Comment
-------------------	-------------	---	---------

Cycle 1, Day 1	0 hr (up to 30 min pre-dose)	24 patients	Pre-FFX infusion
Cycle 1, Day 3	After completion of last dose of all study drugs (+ 30 min)	24 patients	Post-FFX infusion

ECG Analysis

A Full ECG Analysis in:

Up to 24 patients receiving devimistat plus modified FFX (i.e. Arm 1) assigned to the full PK analysis sub-study will also undergo a full ECG analysis. 12-lead ECGs will be recorded at defined intervals (see Table 14 below) from 30 minutes prior to dosing of devimistat on Cycle 1, Day 1 to 6 hours after dosing on Day 1. Subjects will be placed in a supine position for at least 10 minutes prior to timepoints for ECG and PK sampling. ECG recordings will be taken immediately prior to PK sample draw at each time point. **ECG intervals for this full ECG analysis will be measured at a central ECG laboratory fully blinded to timepoints and subject identification.** 12-lead ECGs in these patients will be recorded using a Global Instrumentation (Manlius, NY, USA) M12R ECG continuous 12-lead digital recorder. For Cycle 1, Day 1 (9 time points) and Cycle 1, Day 3 (9 time points), continuous 12-lead digital ECG data will be recorded and stored onto SD memory cards. ECGs will be uploaded onto a central ERT server. Safety ECGs can be printed on-site with the same device. At each protocol-specified timepoint, QT and RR intervals will be measured from up to 10 replicate ECGs. The QTc interval will be derived using Fridericia's formula from the preceding RR interval and the QT interval in each beat and the median QTcF in each replicate will be calculated. The mean across medians from all replicates will be used as the subject's reportable value at that timepoint. All medications administered to subjects from 4 hours prior to the first EKG reading through all time points will be recorded (including doses and time of administration). Measurement of PR and QRS intervals will be performed semi-automatically on three sequential beats from each of the three replicates. The mean value will be calculated for each replicate and then the mean of these used as the subject's reportable value at the timepoint (adapted from Darpo et. al.).¹⁹

Time points for ECG recordings are listed in Table 14.

Table 14 Full ECG Measurement Schedule. Time points are counted from the start of CPI-613® (devimistat) IV infusion.

Cycle #, Day #	Timepoints	N	Comment
Cycle 1, Day 1	0 hr. ±15 (pre-dose) 0.25 hr. ±15 min 0.5 hr. ±15 min 1 hr. ±15 min 2 hr. ±15 min 2.5 hr. ±15 min 3 hr. ±15 min 4 hr. ±15 min 6 hr. ±15 min	Up to 24 patients (i.e. same patients on Arm 1 for Full PK analysis)	Pre-devimistat infusion
Cycle 1, Day 3	0 hr. ±15 (pre-dose) 0.25 hr. ±15 min 0.5 hr. ±15 min 1 hr. ±15 min 2 hr. ±15 min 2.5 hr. ±15 min 3 hr. ±15 min 4 hr. ±15 min 6 hr. ±15 min	Up to 24 patients above	Pre-infusion

B. Sparse ECG Measurement Schedule:

The remaining patients randomized to CPI-613® (devimistat) plus modified FFX (i.e. Arm 1) and all patients on FFX (i.e. Arm 2) will undergo a Sparse ECG analysis. 12-lead ECGs will be recorded at defined intervals. Subjects will be placed in a supine position for at least 10 minutes prior to timepoints for ECG recording. **This Sparse ECG measurement will be measured at a local ECG laboratory and confirmed by central read.** At each protocol-specified timepoint, QT and RR intervals will be measured from each of the three independent 12-lead ECG recordings (i.e., 3 replicates). The QTc interval will be derived using Fridericia's formula from the preceding RR interval and the QT interval in each beat and the median QTcF in each replicate will be calculated. The mean across medians from all replicates will be used as the subject's reportable value at that timepoint. All medications administered to subjects from 4 hours prior to the first ECG reading through all time points will be recorded (including doses and time of administration). Measurement of PR and QRS intervals will be performed semi-automatically on three sequential beats from each of the three replicates. The mean value will be

calculated for each replicate and then the mean of these used as the subject's reportable value at the timepoint (adapted from Darpo et. al.¹⁹). Time points for sparse ECG recordings are listed in Table 15 below.

Table 15 Sparse ECG measurement schedule.

Cycle #, Day #	Timepoints a = 5 min window between the ECG's	N	Comment on Assessment Timepoint
Cycle 1, Day 1	0 hr. (pre-dose) 0.25 hr. 0.5 hr.	Approx. 476 patients = Remaining 225 patients on Arm 1 + All 250 patients on Arm 2	Arm 1: Pre-devimistat infusion Arm 2: Pre-Oxaliplatin infusion
Cycle 1, Day 3	0 hr. (pre-dose) 0.25 hr. 0.5 hr.	Approx. 476 patients above	Arm 1: Pre-devimistat infusion Arm 2: Just prior to completion of 5-FU infusion
Cycle 2, Day 3	0 hr. (pre-dose) 0.25 hr. 0.5 hr.	Approx. 476 patients above	Arm 1: Pre-devimistat infusion Arm 2: Just prior to completion of 5-FU infusion
Cycle 3, Day 3	0 hr. (pre-dose) 0.25 hr. 0.5 hr.	Approx. 476 patients above	Arm 1: Pre-devimistat infusion Arm 2: Just prior to completion of 5-FU infusion
Cycle 6, Day 3	0 hr. (pre-dose) 0.25 hr. 0.5 hr.	Approx. 476 patients above	Arm 1: Pre-devimistat infusion Arm 2: Just prior to completion of 5-FU infusion

Cycle 9. Day 3	0 hr. (pre-dose) 0.25 hr. 0.5 hr.	Approx. 476 patients above	Arm 1: Pre-devimistat infusion Arm 2: Just prior to completion of 5-FU infusion
Cycle 12. Day 3	0 hr. (pre-dose) 0.25 hr. 0.5 hr.	Approx. 476 patients above	Arm 1: Pre-devimistat infusion Arm 2: Just prior to completion of 5-FU infusion

Blood Sampling for Biomarker Analysis:

The following is for Optional Sampling and “Banking” of Blood and Serum Samples for Biomarker analysis. A separate informed consent will be provided to patients with optional sampling.

Blood samples will be obtained prior to treatment initiation (within 4 weeks prior to 1st dose), as well as prior to each restaging scan.

All samples for biomarkers will be retained for up to 10 years after the end of the study and then destroyed or an extension will be requested from appropriate regulatory authorities and IRB/IECs.

All optional samples and specimens should be shipped to the Central Lab. Mailing address, contact name and phone number will be provided in lab manual.

Administration of Questionnaires / Other Instruments for Patient-Reported Outcomes:

Patient-Reported Outcomes (**PRO**) using the NCCN-FACT Hepatobiliary Symptom Index (FHSI- 18). Summary statistics of the scores will be shown by cycle (pre and post treatment). Scores will be compared between standard and study arms.

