Cycle 1	Day 1	
Devimistat: IV infusion at the rate of 4 mL/min at the dose of 500 mg/m² concurrently with D5W at the rate of 125mL/hour (2.08mL/min) via a central venous catheter
 
mFFX (given immediately after devimistat administration):
 
 - Oxaliplatin at 65 mg/m² given as a 2-hr IV infusion - Folinic acid at 400 mg/m² given as a 90-min (1.5 hr) infusion immediately after oxaliplatin, and concurrently with Irinotecan at 140 mg/m² given as a 90-min IV infusion via a Y-connector. - Flurouracil (5-FU) at 400 mg/m² as bolus followed by a 42-48-hr infusion at 2,400 mg/m², starting immediately after completion of folinic acid and irinotecan
	Day 2	
mFFX:
 
 - Completing the remaining of the 5-FU 42-48-hr infusion starting on Day 1
	Day 3	
mFFX:
 
 - Completing the remaining of the 5-FU 42-48-hr infusion starting on Day 1, 2 and disconnect the 5-FU pump. 
devimistat:
 
 - Devimistat (500 mg/m²), IV infusion at the rate of 4 mL/min via a central venous catheter after completion of 5-FU infusion. Devimistat infusion must be administered concurrently with D5W at the rate of 125mL/hour (2.08mL/min) via a central venous catheter. In the event that time will not permit devimistat administration following 5-FU infusion, devimistat may be administered concurrently with 5-FU via a double lumen port.
	Day 4 (-/+ 24 hours)	Myeloid Growth factor per institutional guidelines
	Days 5 -14	No treatment
Cycle 2 and subsequent Cycles (every 2 weeks)		Same as Cycle 1

Dosing as above will continue for at least 6 months in responding patients with acceptable tolerance to therapy (with dose modifications per protocol as needed) unless a criterion for removal from study occurs. Responding patients upon completion of at least 10 cycles and after having two sequential CT scans showing stable disease (no continued decrease in lesion size) will complete 2 additional cycles (to complete a minimum of 12 cycles) of their assigned treatment.

Following 12 cycle and all the subsequent cycles oxaliplatin can be dropped at the discretion of the treating physician if not already omitted. Cycles will continue until one of the criteria for removal from study are reached (Section 5.3.1).

FOLFIRINOX (Control Arm 2; FFX):

Calculation of the Amount of FOLFIRINOX for Each Patient:

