The amount of each of the drug constituents of FFX is based on the BSA of each patient.

The BSA values will be calculated based on the height and body weight taken during screening and this BSA value is used throughout the study. The BSA values will be calculated based on a standard formula, such as Mosteller formula. **If the subject's body weight changes by >10% from the dose to the next dose, BSA should be recalculated and the dose adjusted.**

The Timing of Dosing (FFX):

FFX is a combination of following 4 drugs:

1. oxaliplatin: day 1
2. folinic acid (calcium folinate or FA): day 1 immediately after oxaliplatin
3. irinotecan: day 1 concurrently with folinic acid
4. flurouracil (5-FU): day 1 bolus followed by a 42-48-hr infusion, starting immediately after completion of folinic acid and irinotecan

Administration of FOLFIRINOX (FFX) (see Table 8 below in detail):

1. oxaliplatin: IV infusion
2. folinic acid (calcium folinate or FA): IV infusion
3. irinotecan: IV infusion
4. flurouracil (5-FU): IV bolus, followed by IV infusion

Maximum Hold Time of FOLFIRINOX (FFX) once Reconstituted before Administration:

As per the manufacturer’s instructions found on locally approved prescribing information.

Handling of FOLFIRINOX (FFX):

As per the manufacturer’s instructions found on locally approved prescribing information.

Disposal of FOLFIRINOX (FFX)

Destroy used vials according to institutional guidelines and in compliance with applicable environmental guidelines. Drug destruction must be adequately documented.

The Table 8 below summarizes the administration of FFX.

Table 8 Administration of FOLFIRINOX (FFX) in study Arm 2 for Patients with Metastatic Pancreatic Cancer

Treatment Cycle		Administration of FOLFIRINOX (FFX) in study Arm 2
Cycle	Day	
Cycle 1	Day 1	FOLFIRINOX (FFX): - Oxaliplatin at 85 mg/m ² given as a 2-hr IV infusion - Folinic acid at 400 mg/m ² given as a 90-min (1.5 hr) infusion immediately after oxaliplatin, and concurrently with irinotecan (Irinotecan at 180 mg/m ² given as a 90-min IV infusion) via a Y-connector. - Flurouracil (5-FU) at 400 mg/m ² as bolus followed by a 42-48-hr infusion at 2.400 mg/m ² , starting immediately after completion of folinic acid and irinotecan
	Day 2	FOLFIRINOX (FFX): - Completing the remaining of the 5-FU 42-48-hr infusion starting on Day 1
	Day 3	FOLFIRINOX (FFX): - Completing the remaining of the 5-FU 42-48-hr infusion starting on Day 1,2 and disconnect the 5-FU pump.

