6.5 Additional Analyses

Confidential

For a given cycle, a table will be provided displaying ECG data summarized by treatment arm, day, and timepoint using the safety population, if substantial data exists for Full or Sparse ECG. There will be a table for each cycle.

7. Study Patients

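### Day 3 sparse ECGs carry one set of pre-dose labels in both arms but differ in anchor and often in 5-FU status, and the SAP 6.5 table has no rule to separate them

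*Protocol*

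**What the plan says.** Protocol 7.1.1, Table 15, schedules sparse ECGs on Cycle 1 Day 1 and on Day 3 of Cycles 1, 2, 3, 6, 9 and 12. Every row has the same three labels for both arms: "0 hr. (pre-dose) 0.25 hr. 0.5 hr". On each Day 3 row the comment column gives "Arm 1: Pre-devimistat infusion" for one arm and "Arm 2: Just prior to completion of 5-FU infusion" for the other.

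The treatment tables in Protocol 6.1.5 show what happens on that day. In Arm 1 (Table 7) devimistat is given as "IV infusion at the rate of 4 mL/min via a central venous catheter after completion of 5-FU infusion", with concurrent 5-FU through a double lumen port allowed when time is short. In Arm 2 (Table 8) the only Day 3 entry is "Completing the remaining of the 5-FU 42-48-hr infusion starting on Day 1,2 and disconnect the 5-FU pump".

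The caption of the Arm 1 full ECG table fixes its clock: "Table 14 Full ECG Measurement Schedule. Time points are counted from the start of CPI-613® (devimistat) IV infusion". The sparse caption, "Table 15 Sparse ECG measurement schedule", does not.

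SAP 6.5 plans one table per cycle, if there are substantial data, "displaying ECG data summarized by treatment arm, day, and timepoint using the safety population". QTc is listed with adverse events under the safety endpoint in Protocol 4.2.2. The synopsis notes say that all Arm 2 patients have sparse ECGs to monitor cardiotoxicity.

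**The concern.** Someone reading the SAP 6.5 table will assume that two cells in the same row, one per arm, were measured under the same conditions. On Day 3 they need not have been. The Arm 2 value at 0 hr is taken with 5-FU running. The Arm 1 value is normally taken around or after the end of 5-FU, and on some days during it.

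Arm 2 has no other scheduled on-treatment ECGs, since the full ECG schedule covers Arm 1 only. If these controls are read as like-for-like, a difference in 5-FU status could be mistaken for a treatment difference in QTc, or could hide one. The same risk arises if someone later takes the Day 3 0 hr reading as a within-day reference, because that reference would mean different things in the two arms.

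**Working it through.** The plan states no figure for this point, so the check is mainly a comparison of sections.

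**1. Extent.** Table 15 has 7 ECG days with 3 readings each, so 7 × 3 = 21 readings per patient. Six of the days are Day 3, so 6 × 3 = 18 readings carry the shared labels with different anchors. The table gives about 476 patients. Its own components are 225 + 250 = 475; with 24 full-ECG patients removed from 250, they are 226 + 250 = 476. The two agree to rounding. This is the number scheduled at the start; fewer will remain by Cycles 6, 9 and 12.

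**2. 5-FU status under each Day 3 label.**
- Arm 1, default order: devimistat follows 5-FU, so 0.25 and 0.5 hr fall after 5-FU has stopped. At 0 hr 5-FU has normally stopped too, but Table 15 does not require the ECG to follow pump disconnection.
- Arm 1, concurrent option: 5-FU is running at the start of devimistat. Its status at 0.25 and 0.5 hr depends on when the pump stops.
- Arm 2: 5-FU is running at 0 hr by definition. If the clock starts at the 0 hr ECG, 0.25 and 0.5 hr fall around or after the end of 5-FU. If it starts at the end of 5-FU, both fall after it. Table 15 does not say which.

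**3. Position of the Arm 1 readings relative to devimistat.** Inputs are 500 mg/m², dilution to 12.5 mg/mL (Protocol 6.1.4) and 4 mL/min. Infusion time = (500 × BSA ÷ 12.5) ÷ 4 = 10 × BSA minutes. BSA is not given; 1.8 m² is assumed, with a range of 1.4 to 2.4.
- At 1.8 m²: 18 min.
- At 1.4 m²: 14 min. At 2.4 m²: 24 min.

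If the Arm 1 clock starts with the infusion, as in Table 14, the 0.25 hr ECG (15 min) falls between 1 min after and 9 min before the end of infusion. The 0.5 hr ECG (30 min) falls 6 to 16 min after it. The same two labels in Arm 2 follow no dose.

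**4. What is unaffected.** On Cycle 1 Day 1 the 0 hr ECG precedes devimistat in Arm 1 and oxaliplatin in Arm 2, so both arms are untreated. SAP 5.6 defines baseline as the last non-missing value before treatment, which will normally be this ECG. SAP 6.5 does not use it.

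**5. A common anchor elsewhere.** For Day 3 troponin, Protocol 7.1.1 times both arms from completion of the last dose of all study drugs. The ECG table has no equivalent.

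**The case against.** The strongest reply is that no planned analysis depends on the match. SAP 6.5 is descriptive and conditional on enough data. It refers to ECG data rather than QTc, and it plans no between-arm test and no change from the Day 3 0 hr value. The safety outcomes in Protocol 9.4.4 are all based on adverse events. All of this is correct, and it limits the point to how a table will be read.

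The Arm 2 anchor can also be defended. A recording made while 5-FU is running serves cardiotoxicity monitoring, and moving every Arm 2 Day 3 ECG to after disconnection would lose the only reading that Table 15 places during 5-FU. That is a real trade-off, so re-timing is not the obvious remedy.

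Nor is a new data field needed. The sparse ECG text in Protocol 7.1.1 already requires medications to be recorded with doses and times, from 4 hours before the first ECG through all timepoints.

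Finally, Arm 2 could not isolate devimistat in any case, because oxaliplatin and irinotecan doses differ between the arms. That stands too, but it does not make readings with different 5-FU status interchangeable. None of these replies supplies the missing time origin or a rule for the SAP table.

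**Conclusion.** The point holds as a problem of labelling and presentation in a secondary safety endpoint. On six of seven sparse ECG days the same label covers different anchors and, by default, different 5-FU status at 0 hr. Arm 2 has no Day 3 dose for the pre-dose label to refer to.

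Two stronger readings are tempting, and the documents support neither.
- A reader might infer a QTc bias of a known size. The documents give neither a 5-FU effect on QTc nor the interval between pump stop and the Arm 1 ECG. Both 0 hr readings sit near the end of a 42 to 48 hour infusion, so any difference may be small.
- A reader might take a rise from 0 to 0.5 hr in Arm 1 as the effect of devimistat and the same-labelled change in Arm 2 as its control. In Arm 1 5-FU has either just stopped or is still running, so that change does not isolate devimistat, and no such comparison is planned.

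The conclusion rests on the default order in Table 7 being the usual one. The more often devimistat runs concurrently with 5-FU, the closer the arms are at 0 hr and the more mixed the Arm 1 column becomes.

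**What to change.** In SAP 6.5:
- Report QTcF change from the Cycle 1 Day 1 pre-dose value, using the baseline that SAP 5.6 already defines.
- State that the Day 3 0 hr ECG is not a common reference across arms.
- Label or split Day 3 readings by whether 5-FU was running or had stopped, derived from the recorded medication times, and show readings with missing times separately.

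The baseline change gives both arms the same untreated reference. It does not remove the difference in 5-FU status at the later reading, so the split is needed as well.

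In Protocol Table 15, state the time origin for each arm and reconcile the two Day 3 anchors. Which anchor to use is for the sponsor to decide.

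The cost is a small amount of extra programming and some table wording, with no additional ECGs and no new data field. The SAP changes also work for ECGs already taken, provided the medication times were recorded; the Table 15 wording helps only those still to come.
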